3.4. Stopping Rules for the Study

There are no formal rules for early termination of this study. During the conduct of the study, serious adverse events will be reviewed as they are reported from the investigational centers to identify safety concerns (Section 7.1.5).

The study may be terminated by the sponsor for any reason at any time. For example, the sponsor should terminate the study in the event of:

- new toxicological or pharmacological findings or safety issues invalidating the earlier positive benefit-risk assessment
- discontinuation of the development of the IMP
- the number of severe CE-COPDs collected

If the whole study will be stopped, the patients that are terminated early will be followed according to Withdrawal Criteria and Procedures for the Patient (Section [4.3](#)).

3.5. Schedule of Study Procedures and Assessments

Study procedures and assessments with their time points are presented in [Table 1](#). Detailed descriptions of each procedure and assessment are provided in Section [6](#) (endpoint assessments) and Section [7](#) (safety assessments). Study procedures and assessments by visit are listed in [Appendix B](#).

Table 1: Study Procedures and Assessments

Study period	Pre-intervention						Intervention					
	V1	V2	V3 ^a	V4 ^a	Vz	V5	Day -14 to Day 1	Day 1	Day 28 ±7 days	Day 56 ± 7 days	Up to 14 days after CE-COPD start date	Day 84 ±14 days
Day and allowed time windows												
Procedures and assessments	Screening	Baseline	Phone visit	Phone visit	Exacerbation visit	Final/early termination visit						
Informed consent	X											
Inclusion and exclusion criteria	X	X										
Assign patient number	X											
Medical history	X											
Prior medication and treatment history	X											
Physical examination, including height and weight ^b	X				X	X						
Vital signs measurement ^c	X											
Urine pregnancy test for women of childbearing potential	X										X	
Inform patients of study compliance for eMDPI and accelerometer and requirement for provider visit in the event of CE-COPD	X	X	X	X								
Assess for COPD exacerbations	X	X	X	X							X	
Adverse events inquiry		X	X	X	X						X	
Wearable accelerometers: dispense, training, and collection ^d		X										X
ABS eMDPI: dispense, training, collection, and accountability ^e		X				X						X
Concomitant medication inquiry	X	X	X	X	X	X						

^a Investigational centers must obtain source documentation for all COPD exacerbations that occur during the treatment period to confirm the accuracy of the information obtained from the patient.

^b Height will be measured at the screening visit only.

^c Vital signs measurements will include blood pressure, respiratory rate, and heart rate.

^d Wearable accelerometers for a subset of patients who agree to participate at specific investigational centers will be dispensed at visit 2, and SDI and TDS data will be collected continuously from visit 2 through visit 5 via the wearable accelerometer. Instructions for proper use of the devices will be provided to patients at visit 2. The devices will be collected at visit 5.

^e Patients will receive initial eMDPI devices at visit 2 based on anticipated usage pattern. In the event that additional eMDPI devices are needed, patients will be required to visit the investigational center to receive them. Patients will be instructed to return all inhalers to the investigational center at the last study visit or earlier, including at the early termination visit, as well as at any other point if there is a problem with the inhaler. Instructions for dispensing, proper clinical use, and collecting ABS eMDPI will be provided to patients at visit 2 and reviewed during the monthly calls.

ABS = albuterol sulfate; CE-COPD = clinical exacerbation of chronic obstructive pulmonary disease; COPD= chronic obstructive pulmonary disease; eMDPI=multidose dry powder inhaler with an eModule; SDI = sleep disruption index; TDS=total daily step; V = visit.

Note: Screening and baseline visits may be combined.

4. SELECTION AND WITHDRAWAL OF PATIENTS

Prospective waivers (exceptions) from study inclusion and exclusion criteria to allow patients to be enrolled are not granted by Teva ([Appendix C](#)).

4.1. Patient Inclusion Criteria

Patients may be enrolled in this study only if they meet all of the following criteria:

- a. The patient is male or female, 40 years of age or older, with a physician diagnosis of COPD. The diagnosis should include a history of FEV₁/forced vital capacity <70% predicted and FEV₁ <80% predicted documented in the patient's chart.
- b. The patient is currently using a SABA reliever plus at least one of the following: long-acting beta agonist (LABA), an ICS/LABA, a long-acting muscarinic antagonist (LAMA), or a LABA/LAMA.
- c. The patient has had at least 1 episode of moderate or severe CE-COPD as described in Section [6.1.1](#) over the past 12 months before screening.
- d. The patient must be able to demonstrate appropriate use of albuterol from the ABS eMDPI.
- e. The patient is able to provide written informed consent.
- f. The patient must be willing and able to comply with study requirements as specified in the protocol, including the use of a wearable accelerometer for the subset of patients who consent to use of the device.
- g. The patient is willing to discontinue all other rescue or maintenance SABA or short-acting anti-muscarinic agents and replace them with the study-provided ABS eMDPI for the duration of the trial.
- h. Women of childbearing potential (not surgically sterile or ≥2 years postmenopausal) must have exclusively same-sex partners or use a highly effective or acceptable method of birth control and must agree to continue the use of this method for the duration of the study and for 30 days after discontinuation of the IMP. Highly effective methods of birth control are defined as those, alone or in combination, that result in a low failure rate (ie, <1% per year) when used consistently and correctly. Highly effective methods of birth control in this study include combined (estrogen- and progestogen-containing) or progestogen-only hormonal contraception associated with inhibition of ovulation, intrauterine device, intrauterine hormone-releasing system, bilateral tubal occlusion, vasectomized partner, and sexual abstinence. Acceptable birth control methods that result in a failure rate of more than 1% per year include: progestogen-only oral hormonal contraception, for which the inhibition of ovulation is not the primary mode of action; male or female condom with or without spermicide; and cap, diaphragm, or sponge with spermicide. The combination of male condom with either cap, diaphragm, or sponge with spermicide (double barrier methods) are also considered acceptable, but not highly effective, methods of birth control. Additional details can be found in [Appendix E](#).

4.2. Patient Exclusion Criteria

Patients will not be enrolled in this study if they meet any of the following criteria:

- a. The patient has any clinically significant medical condition (treated or untreated) that, in the opinion of the investigator, would interfere with participation in the study.
- b. The patient has any other confounding underlying lung disorder other than COPD.
- c. The patient has used an investigational drug within 5 half-lives of it being discontinued, or within 1 month of visit 2, whichever is longer.
- d. The patient is a pregnant or lactating woman or plans to become pregnant during the study. Note: Any woman becoming pregnant during the study will be withdrawn from the study.
- e. The patient is either an employee or an immediate relative of an employee of the investigational center.
- f. The patient is known to be allergic to albuterol or any of the excipients in the IMP or rescue medication formulation (ie, lactose [milk protein]). Dietary lactose intolerance does not exclude the patient from inclusion in the study or as per the investigator's medical discretion.
- g. The patient has a history of drug or alcohol abuse within 2 years prior to the screening visit.
- h. The patient has a history of positive testing for human immunodeficiency virus types 1 and 2, hepatitis B, hepatitis C, and tuberculosis. Note: A history of a positive tuberculosis skin test without active tuberculosis may be acceptable only if the patient has received an accepted prophylactic treatment regimen and has no clinical evidence of active disease. Patients with a history of hepatitis C who have undergone treatment and achieved a sustained virologic response may be eligible if they meet all other selection criteria and receive medical monitor approval.
 - i. The patient has symptomatic congestive heart failure.
 - j. A member of the patient's household is participating in the study at the same time.

4.3. Withdrawal Criteria and Procedures for the Patient

Each patient is free to withdraw from the study at any time, without prejudice to their continued care. Patients must be withdrawn from the study if any of the following events occur:

- a. Patient withdraws consent or requests discontinuation from the study for any reason.
- b. Patient develops an illness that would interfere with his/her continued participation.
- c. Patient is noncompliant with the study procedures and assessments or administration of ABS eMDPI, in the opinion of the investigator.
- d. Patient takes prohibited concomitant medications as defined in this protocol.
- e. A female patient has a confirmation of pregnancy during the study from a positive pregnancy test.

- f. The sponsor requests withdrawal of the patient.
- g. Patient experiences an adverse event or other medical condition that indicates to the investigator that continued participation is not in the best interest of the patient.

Patients should be treated with standard of care after withdrawal from or termination of the study, as appropriate.

Investigators should attempt to obtain information on patients in the case of withdrawal or discontinuation. Results of any evaluations and observations, together with a narrative describing the reason(s) for withdrawal, must be recorded in the source documents. The electronic case report form (eCRF) must document the primary reason for withdrawal or discontinuation.

See [Appendix F](#) for information regarding how the study will define and address patients who are lost to follow-up to help limit the amount and impact of missing data.

If the reason for withdrawal is an adverse event, monitoring will be continued as applicable (eg, until the event has resolved or stabilized, until the patient is referred to the care of a healthcare professional, or until a determination of a cause unrelated to the IMP or study procedure is made). The specific event or test result (including repeated test results, as applicable) must be recorded both on the source documentation and in the eCRF; both the adverse events eCRF and termination eCRF will be completed at that time.

All assessments should be performed according to the protocol for the final visit or early termination (visit 5) if possible. Patients are required to return the ABS eMDPI (used and unused) upon withdrawal from the study.

4.4. Replacement of Patients

A patient who is enrolled but does not complete the 12-week intervention period will not be replaced.

4.5. Rescreening

A patient who is screened but not enrolled (eg, because inclusion and exclusion criteria were not met or enrollment did not occur within the specified time) may be considered for screening again if, eg, there is a change in the patient's medical background or a modification of study inclusion and exclusion criteria.

If the patient is rescreened, an informed consent form (ICF) will need to be re-signed.

4.6. Screening Failure

Screening failures are defined as participants who consent to participate in the clinical study but are not subsequently enrolled. Minimal information includes, but is not limited to, demography, screening failure details, eligibility criteria, and any serious adverse events.

5. TREATMENTS

5.1. Investigational Medicinal Products Used in the Study

Patients will receive initial eMDPI devices at visit 2 based on anticipated usage pattern. In the event that additional eMDPI devices are needed, patients will be required to visit the investigational center to receive them. Patients will be instructed on proper use of the device, including the requirement for use within 60 seconds of opening the cap. Patients will be instructed to return all inhalers to the investigational center at the last study visit or earlier, including at the early termination visit (visit 5), as well as at any other point if there is a problem with the inhaler. Compliance to ABS eMDPI administration will be monitored.

5.1.1. Test Investigational Medicinal Product

ABS eMDPI is an inhalation-driven MDPI containing a blend of ABS and alpha-lactose monohydrate. The inhaler contains 200 actuations, each delivering 90 mcg of albuterol base ex-mouthpiece; the inhaler is equipped with a dose counter that shows only even numbers and counts down to “0”.

The plastic inhaler comprises a reservoir containing inhalation powder, a metering system, a mouthpiece with dust cover, and an eModule sitting on top of the drug delivery compartment. The on-board electronics and power source are fully integrated into the inhaler and are designed to operate for the life of the inhaler without intervention. The electronic module records timestamped, predefined events such as cap opening and inhalation.

Additional details may be found in [Table 2](#) and in the IB.

5.1.1.1. Starting Dose and Dose Levels

The prescribed dose will be 90 mcg, 1 to 2 inhalations every 4 hours as needed. No dose escalations are planned.

5.1.1.2. Dose Modification and Dose Stratification

Not applicable.

5.1.2. Reference Investigational Medicinal Product

Not applicable.

5.1.3. Placebo Investigational Medicinal Product

Not applicable.

Table 2: Investigational Medicinal Products Used in the Study

IMP name	Test IMP	Placebo IMP	Reference IMP
Trade name	ABS eMDPI	Not applicable	Not applicable
Formulation	Inhalation powder	Not applicable	Not applicable
Unit dose strength	90 mcg	Not applicable	Not applicable
Route of administration	Inhalation	Not applicable	Not applicable
Dosing instructions	1 to 2 inhalations every 4 hours as needed	Not applicable	Not applicable
Packaging	IMP will be provided in a box	Not applicable	Not applicable
Manufacturer	Teva Pharmaceutical Industries, Ltd. Jerusalem, Israel	Not applicable	Not applicable

ABS=albuterol sulfate; eMDPI=multidose dry powder inhaler with an eModule; IMP=Investigational Medicinal Product; Ltd=limited.

5.2. Preparation, Handling, Labeling, Storage, and Accountability for Investigational Medicinal Products

5.2.1. Storage and Security

The investigator or designee must confirm that appropriate temperature conditions have been maintained for all IMPs received, and any discrepancies are reported and resolved before use of the IMP.

The IMP must be stored at monitored room temperature (15°C to 25°C [59°F to 77°F]) and not exposed to extreme heat, cold, or humidity.

5.2.2. Labeling

Supplies of IMP will be labeled according to the current International Council for Harmonisation (ICH) guidelines on Good Clinical Practice (GCP) and Good Manufacturing Practice and will include any locally required statements.

5.2.3. Accountability

Each IMP shipment will include a packing slip listing the contents of the shipment, return instructions, and any applicable forms.

The investigator is responsible for ensuring that deliveries of IMPs for initial distribution to patients and other study materials from the sponsor are correctly received, recorded, handled, and safely and properly stored in accordance with the Code of Federal Regulations (CFR) and used in accordance with this protocol. All additional dispensing of the IMP will take place at the investigational center as needed.

Only patients enrolled in the study may receive IMP. The investigator (or designee) will instruct the patient to store the IMP according to the instructions on the label, if applicable, or will give instructions in an appropriate form. Patients will be instructed to return all IMP (empty, partially

used, and unused inhalers) to the investigational center at the final visit or earlier, including at the early termination visit, as well as at any other point if there is a problem with the inhaler.

The investigator, institution, or the head of the medical institution (where applicable) is responsible for IMP accountability, reconciliation, and record maintenance (ie, receipt, reconciliation, and final disposition records). Patients will return all inhalers at the end of the study to the investigational center for reconciliation.

A record of IMP accountability (ie, IMP and other study materials received, used, retained, and returned) must be prepared and signed by the principal investigator or designee, with an account given for any discrepancies. Empty, partially used, and unused inhalers will be disposed of at the end of the study following collection of data from the device and with sponsor's approval.

Further guidance and information may be provided in the Study Reference Manual.

5.3. Justification for Investigational Medicinal Products

5.3.1. Justification for Dose of Test Investigational Medicinal Product

The prescribed dose of ABS eMDPI used in this study (ie, 90 mcg, 1 to 2 inhalations every 4 hours as needed) was selected based on the prescribing information for PROAIR® RESPICLICK, which has the same drug delivery design as ABS eMDPI.

PROAIR® RESPICLICK is indicated in patients 4 years of age and older for the treatment or prevention of bronchospasm with reversible obstructive airway disease and for the prevention of EIB. For the relief of acute bronchospasm symptoms, PROAIR® RESPICLICK is recommended at a dosage of 2 inhalations (ie, 180 mcg of albuterol base ex-mouthpiece) repeated every 4 to 6 hours. More frequent administration or a larger number of inhalations is not recommended. In some patients, 1 inhalation every 4 hours may be sufficient. The recommended dosage for PROAIR® RESPICLICK for prevention of EIB in adults and children 4 years of age or older is 2 inhalations 15 to 30 minutes before exercise. To date, the overall results of clinical studies provide robust and consistent evidence that PROAIR® RESPICLICK is effective for the treatment or prevention of bronchospasm in adult and adolescent patients with obstructive airway disease.

5.4. Treatment After the End of the Study

No treatment is planned by the sponsor after the end of the study. Patients should be treated with standard of care after withdrawal from or termination of the study, as appropriate.

5.5. Restrictions

There are no additional restrictions beyond the inclusion and exclusion criteria in this study.

5.6. Prior and Concomitant Medication or Therapy

Any prior or concomitant medication a patient has had within 30 days before enrollment and up to the end of study will be recorded on the eCRF. Trade name and international nonproprietary name (if available), indication, dose, and start and end dates of the administered medication will

be recorded. The sponsor will encode all medication according to the World Health Organization drug dictionary.

The following medications will be prohibited during this study:

- any immunosuppressive or immunomodulatory agents including, but not limited to, methotrexate, cyclosporine, and interferon- α for 2 months prior to Visit 2
- levalbuterol during the 12-week intervention period
- other forms of albuterol MDI during the 12-week intervention period
- any rescue nebulizer (SABA, SAMA or SABA/SAMA) outside of a CE-COPD

At each investigational center visit and during monthly phone calls, the patients will be asked whether they have taken any medications (other than IMP), including over-the-counter medications, vitamins, or herbal or nutritional supplements, since the previous visit.

Concomitant medication and treatment will be recorded through visit 5.

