3. STUDY DESIGN

3.1. General Design

This is a 12-week, multicenter, open-label study to evaluate the relationship between as-needed usage of ABS eMDPI and CE-COPD in adult patients at least 40 years of age with exacerbation-prone COPD. ABS eMDPI is a rescue/reliever agent that includes an eModule on top of the approved PROAIR® RESPICLICK inhaler. The on-board electronics and power source are fully integrated into the inhaler and are designed to operate for the life of the inhaler without intervention. The electronic module records timestamped, pre-defined events such as cap open and inhalation parameters. The inclusion of the eModule has been shown to have no impact on the dose delivery compared with the approved product without the eModule.

The study will consist of a screening period of up to 2 weeks and a 12-week intervention period.

After providing written informed consent, patients will complete a screening visit (visit 1) to determine eligibility for the study. Patients will provide medical history (including prior medications), complete a physical examination, pregnancy test, if applicable, and review COPD exacerbation history. Eligible patients will return to the investigational center within 2 weeks for the baseline visit (visit 2). Those meeting entry criteria will be trained on the use of the eMDPI device and, upon demonstrated competency, will receive ABS eMDPI devices for use as rescue bronchodilators during the study. The screening visit and baseline visit may be combined.

Patients must use ABS eMDPI as their only rescue agent for the duration of their participation in this study and will be advised to place any current rescue pills, inhalers, or nebulizers, including SABA, short-acting muscarinic antagonists (SAMAs), or SABA/SAMA combination into storage. Patients may continue the use of other COPD and non-COPD medications as advised by their physician without changes unless deemed necessary by their physician. Patients will be managed according to routine clinical practice by their treating physician with no specific study-related instructions provided other than those on the proper use of ABS eMDPI.

Patients will be contacted by phone on a monthly basis for the collection of information about COPD exacerbations and treatments, concomitant medications, and adverse events. A review of the instructions for the use of ABS eMDPI and the procedure for replacement and return of ABS eMDPI will also occur during the monthly call.

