6.1.2. Albuterol Use

Albuterol usage data will be downloaded using extraction software directly from eMDPI devices collected from the patients at their final study visit after return of the device to the depot.

For albuterol use, parameters of interest will include (1) the total number of inhalations in the days preceding the peak of a CE-COPD, (2) the number of days prior to the peak of a CE-COPD when albuterol use increased, and (3) the number of albuterol uses in the 24 hours preceding a CE-COPD.

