7.1.2. Analysis Methods for Albuterol Use

7.1.2.1. Pattern of Baseline Daily and Weekly Albuterol Use

A patient's pattern of baseline albuterol use is exhibited if, on any given day, during a given week, they do not take more than their average number of inhalations computed from day 1 to day 7.

Summary statistics including 95% CIs intervals of the proportion of patients exhibiting their individual weekly baseline albuterol use during each week of the 12 week study (Week 1, Week 2,..., Week 12) will be presented overall and by CE-COPD status and by CE-COPD severity (Yes: severe, moderate; No).

Summary statistics including 95% CIs intervals of the proportion of eMDPI time on study days when a patient did not take more than the average number of inhalations computed from day 1 to day 7 (number of days a given patient had no more than average baseline albuterol use) / total number of eMDPI study days for a given patient) will be summarized overall and by CE-COPD status and by CE-COPD severity (Yes: severe, moderate; No).

Week 1 and Week 2 and the first 14 day patient albuterol use patterns, "WK1:I#iD#dMTN#n," "WK2:I#iD#dMTN#n" and "D14:I#iD#dMTN#n" designation, will be summarized descriptively (counts and percent) overall and by CE-COPD status and by CE-COPD severity (Yes: severe, moderate; No).

7.1.2.2. Total Number of Inhalations in the Days Preceding the Peak of a CE-COPD

For patients who experienced a CE-COPD, summary descriptive statistics of the total number of inhalations taken in 1 day (eg, the 24-hour period on the day prior to the date of the CE-COPD symptom peak) and at 3, 5, 7, 10, 14, and 21 days preceding the date of the CE-COPD symptom peak, will be presented overall and by moderate CE-COPDs and severe CE-COPDs.

In this analysis, among patients experiencing more than 1 CE-COPD, the subsequent CE-COPDs can be considered a separate CE-COPD, distinct from the first (preceding) CE-COPD, provided the patient exhibited at least 1 day of baseline albuterol use after the first (preceding) CE-COPD's end date, as captured on the adverse event page, and prior to the subsequent CE-COPD's start date, as captured on the adverse event page. For patients who experience multiple CE-COPDs, all distinct CE-COPDs will be considered in this descriptive analysis. Descriptive summaries of the number of inhalations on the days prior to a CE-COPD will only be reported if the event does not overlap with a preceding CE-COPD. For example, if the date of symptom

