7.1.2.3. Hypothesis: Albuterol Use Will Increase Several Days Prior to a CE-COPD

The hypothesis under consideration is that albuterol use will increase several days prior to a CE-COPD. Several days will be defined as 7 days prior to the date of the CE-COPD symptom peak for this analysis.

For each subject that experiences at least 1 CE-COPD, Y_1, \dots, Y_7 will represent the number of puffs of albuterol during the 7 days preceding the date of the CE-COPD symptom peak and Y_8, \dots, Y_{14} will represent the number of puffs taken each day during days 8 through 14 preceding the date of the CE-COPD symptom peak. Under the hypothesis of no increased albuterol use

preceding an exacerbation (ie, null hypothesis) assume for subject "xxx" that $Y_i \stackrel{iid}{\sim} \text{Poisson}(\lambda_{xxx})$ for all subjects i. Alternatively, if albuterol use does increase prior to an exacerbation, then

$Y_i \stackrel{iid}{\sim} \text{Poisson}(\lambda_{xxx})$ during day 8 through 14 preceding the date of the CE-COPD symptom peak

and $Y_i \stackrel{iid}{\sim} \text{Poisson}(\lambda_{xxx} + \delta)$ for the immediate 7 days preceding the CE-COPD(s). Also, for random subject effect, assume λ_{xxx} follows some distribution to account for subject to subject variability. Let d_{xxx} will equal to the mean number of puffs during the 7 days immediately preceding the date of the CE-COPD symptom peak minus mean number of puffs during days 8 through 14 preceding the date of the CE-COPD symptom peak. To assess if albuterol usage increases 7 days prior to a CE-COPD, $H_0: \mu_D = 0$, $H_1: \mu_D > 0$ will be tested using a t-test at the 0.05 significance level.

7.1.2.4. Number of Days Prior to the Peak of a CE-COPD When Albuterol Use Increased

Among patients who experienced a CE-COPD, summary statistics of the number of days prior to the peak of a CE-COPD when albuterol use increased, will be presented overall and by moderate CE-COPDs and severe CE-COPDs for 3 thresholds defining an increase in albuterol use;

- (i) First occurrence of a single day increase of 20% from baseline use prior to CE-COPD
- (ii) First occurrence of a single day absolute increase of 2 inhalations from baseline use prior to CE-COPD
- (iii) First occurrence of a single day absolute increase of 4 inhalations from baseline use prior to CE-COPD

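### The protocol conflicts with itself on nebulizer rescue during a CE-COPD, and the peak-anchored albuterol counts have no rule for days when other rescue replaces the study inhaler

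*Protocol*

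**What the plan says.** **Rescue rule.** Protocol 3.1 states: "Patients must use ABS eMDPI as their only rescue agent for the duration of their participation in this study". It also asks patients to put other rescue products, nebulizers included, into storage. Inclusion criterion g asks for willingness to give up all other SABA and short-acting antimuscarinic agents for the trial. Neither place makes an exception for an exacerbation. The prohibited list in Protocol 5.6 contains "any rescue nebulizer (SABA, SAMA or SABA/SAMA) outside of a CE-COPD", so by implication a nebulizer is not prohibited during a CE-COPD. Protocol 4.3 d makes withdrawal mandatory for a patient who takes prohibited medication.

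**What is counted.** Protocol 6.1.2: "Albuterol usage data will be downloaded using extraction software directly from eMDPI devices". Other medicines go on the eCRF with "indication, dose, and start and end dates of the administered medication" (Protocol 5.6), but they do not enter the albuterol-use variables.

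**Where the windows end.** SAP 7.1.2.2 plans "summary descriptive statistics of the total number of inhalations taken in 1 day" and at longer intervals back to 21 days before symptom peak, overall and by severity. In SAP 7.1.2.3 the first seven counts "will represent the number of puffs of albuterol during the 7 days preceding the date of the CE-COPD symptom peak" and are compared with days 8 to 14. The section fixes the window in these words: "Several days will be defined as 7 days prior to the date of the CE-COPD symptom peak for this analysis". The 24-hour maximum in SAP 7.1.1 also runs up to the peak. The missing-data rules in SAP 4.6 do not mention days on which rescue came from another source or the patient was an inpatient, and SAP 8 plans no sensitivity analysis.

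**The concern.** There are two linked problems.

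The first is conduct. A site working from 3.1 or criterion g would see a nebulizer used during an exacerbation as a breach. A site working from 5.6 would not. Since 4.3 d ties withdrawal to prohibited medication, the difference can decide whether a patient stays in the study at the time of the outcome event.

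The second is measurement. Days between symptom onset and symptom peak lie inside the peak-anchored windows. If nebulized or inpatient rescue replaces the inhaler on those days, the download shows fewer inhalations just when need is greatest. The 7.1.2.3 test, which carries the study's stated hypothesis, would then be biased toward no increase. Severe events are defined by hospitalization, so if admission comes before the peak they could be affected more than moderate ones and appear to have a smaller rise.

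**Working it through.** **1. The plan's own figures.** The documents give no frequency for nebulizer use and no onset-to-peak interval. The related design figure is the expected event count. 360 × 1.095 × 12/52 = 90.97, where 1.095 is the midpoint of 1.05 and 1.14 per year. This matches the stated 91. The Poisson 2.5% and 97.5% points are 73 and 110, and P(at least 70) = 0.9901, also as stated. None of these is affected here. The severe share is stated as 14%.

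**2. Effect on one event, assuming use doubles for the whole week.** Assume 4 inhalations a day on days 8–14 and a true 8 a day on days 1–7 before peak, a true difference of +4.0. Let a share f of rescue be replaced on k of the last 7 days.

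Recorded difference = [(7 − k) × 8 + k × 8 × (1 − f)]/7 − 4

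- k = 3, f = 0.5: 6.29 − 4 = +2.29 (43% lost)
- k = 3, f = 1: 4.57 − 4 = +0.57 (86% lost)
- k = 4, f = 1: 3.43 − 4 = −0.57

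**3. Effect on the mean.** The test averages over patients, so these losses must be weighted by the share affected, π. Take π = 0.14 (severe events only, treating the share of events as the share of patients) with k = 3 and f = 1. The loss per affected event is 24/7 = 3.43. The mean is 4.0 − 0.14 × 3.43 = 3.52, a 12% loss. For the mean to change sign at k = 4, f = 1, π would have to exceed 4/4.57 = 87.5%.

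**4. Effect by severity.** In the same scenario the true 7-day total is 7 × 8 = 56 for both severities. Severe events would record 4 × 8 = 32. The severity columns of 7.1.2.2 would differ with no true difference in rescue use.

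**5. Sensitivity to the shape of the rise.** Now suppose use stays at b a day until onset and rises by r only on the L days from onset to peak, with a share s replaced.

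True rise = L × r/7; recorded rise = L × [r − s(b + r)]/7

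With b = 4, r = 4, L = 2, the true rise is +1.14. It is recorded as +0.57 at s = 25%, 0 at 50% and −1.14 at 100%. Averaged with π = 0.14 and s = 1: 1.14 − 0.14 × (2 × 8/7) = 0.82, a 28% loss. A sign change in the mean needs π × s > r/(b + r), which is 25% to 67% for b = 2 to 6 and r = 2 to 4. All of these exceed 14%. If use also rises by 2 a day before onset (b = 4, r = 4), an event with L = 1 or 2 stays positive even at s = 100% (+1.14 and +0.29).

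**6. Which analyses are exposed.**
- SAP 7.1.1 (24-hour maximum), 7.1.2.2 and 7.1.2.3 run to symptom peak and are exposed.
- SAP 7.1.2.4 also looks back from peak but records the first day of increase. Later substitution does not change it if the rise came earlier.
- SAP 7.5.2.1 compares the same two weeks before symptom onset and requires 14 CE-COPD-free days. With L = 0 the mechanism has no effect, provided the 5.6 exception starts at onset.
- SAP 7.5.2.3 uses only CE-COPD-free days.

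**The case against.** The strongest reply is that the objective concerns albuterol use as captured by the device. On that reading the count is right and only its interpretation after onset is open. This stands as far as it goes: the count is not an error. But the hypothesis treats recorded use as a marker of deterioration, and a count that falls because rescue moved elsewhere is a poor marker on those days.

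Second, the plan already contains a comparison without this problem. SAP 7.5.2.1 applies paired t, Wilcoxon and McNemar tests to the weeks before onset. This also stands, and it shows that the effect comes largely from anchoring at peak. It does not repair 7.1.2.3, which remains planned as it is. The analyses are exploratory with no designated primary endpoint, which limits the consequence.

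A reader might infer three stronger things that the documents do not support:
- **That all albuterol-use analyses are compromised.** Sections 7.5.2.1 and 7.5.2.3 are largely protected, and 7.1.2.4 is less exposed.
- **That the study would show falling use while rescue rises.** The 43%, 86% and sign-change figures apply to a fully affected event. Nothing in the documents says how many events are affected or dates admission relative to peak.
- **That SAMA inhalers or other albuterol forms are allowed because 5.6 does not list them.** Section 3.1 and criterion g bar them, and Protocol 5.5 points back to the entry criteria.

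**Conclusion.** The point holds in a limited form. The conflict between 3.1, criterion g and 5.6 is in the current text and bears on withdrawal under 4.3 d. The peak-anchored summaries and the 7.1.2.3 test have no rule for days when other rescue replaces the inhaler. If that happens within the last 7 days before peak, the recorded rise is biased toward zero, possibly more for severe events.

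The size cannot be known from the documents. With use doubling for the whole week and only severe events losing three days, the mean rise is about 12% too small. If the rise begins only at onset, the proportional loss is larger (28% with the inputs shown). On the severe-only assumption, a change of sign in the mean is unlikely. If many moderate events also involved nebulizers, that assurance would weaken.

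Two further assumptions matter. The documents do not define when a CE-COPD has begun for the purpose of 5.6. And if onset came more than 7 days before peak, the comparison week could be lowered too, and the net bias would be harder to sign.

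**What to change.** 1. Reconcile Protocol 3.1, inclusion criterion g and 5.6 so that sites have one rule on non-study rescue. This review takes no view on which rule is right.
2. In SAP 7.1.2.2 and 7.1.2.3, flag days with recorded non-study SABA or SAMA or an inpatient stay, using the concomitant-medication dates and the hospitalization dates where these are captured. Report the number of flagged days by severity.
3. Repeat the 7.1.2.3 test with flagged days excluded, alongside the planned test and not in place of it. Exclusion alone can remove a real rise: in step 5 of the working, dropping the onset-to-peak days leaves b − b = 0 where the true rise was +1.14.
4. Name the onset-anchored comparison in 7.5.2.1 as the one to rely on if the results differ.

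The cost is a protocol clarification, a short SAP derivation and a change to the statement that no sensitivity analysis is planned. No new visits are needed. The limits are fewer days near the peak, missing for reasons related to severity. As-needed nebulizer use may be recorded only as date ranges, and the documents do not clearly list admission and discharge dates as eCRF items.
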